11.6 Investigator Responsibilities (21CFR312.50 & 21CFR312.53)

The investigator is responsible for ensuring that the investigation is conducted in accordance with the general investigational plan and protocols, maintaining an effective IND with respect to the investigation, and ensuring that FDA and all participating investigators are promptly informed of significant new adverse effects or risks with respect to the drug.

The investigator will maintain a current signed investigator statement (FDA 1572), a current Curriculum Vitae (CV), and a current clinical protocol.

12. STATISTICAL CONSIDERATIONS

- 12.1 Study Design/Primary Endpoints
 - 12.1.1 Establish a safe dose for oral 5-ALA administration NCI Common Toxicity Criteria will be used to quantify toxicity following 5-ALA administration. Special attention will be paid to rash, pruritis, hepatic transaminitis, nausea and vomiting. Based on previously reported German trial, a 30 mg/kg dose is anticipated to be as well-tolerated as 10 and 20 mg/kg doses.
 - 12.1.2 Determine the sensitivity and specificity of the Phase 1 recommended dose in discriminating between normal and malignant tissue intraoperatively.

Four methods are being employed to assess discrimination of tumor from normal brain tissue.

- The neurosurgeon will assess the ability to distinguish tumor from normal brain tissue under ultraviolet illumination and grade the discrimination from 0 to +++ (3+) (See Section 8.1.1). Although arguably the most relevant measure, this is also the most biased and difficult to corroborate measure.
- Under white light the neurosurgeon will assess and biopsy an area of obvious tumor and an area of obviously normal (but possibly edematous) non-eloquent brain. The neurosurgeon will then assess whether these

IRB NUMBER: 12-135

- areas correspond to areas of strong, weak or no fluorescence seen under blue light.
- Under blue light, the neurosurgeon will assess the areas of fluorescence in the tumor cavity and will biopsy areas of strong fluorescence, weak fluorescence and no fluorescence. It may not be necessary to repeat some of these biopsies if the area has already been biopsied under white light. The pathologist will score tumor involvement in each biopsy specimen.

These data will be placed in the following grids – first a 3x3 grid as follows for an analysis of correlation, specifically a Cohen's kappa will be calculated to assess the strength of agreement between fluorescence and tumor density:

Fluorescence vs. Tumor Density	Solid Tumor	Infiltrating tumor/normal brain	No tumor (edematous peritumoral normal brain)
High Fluorescence	(Number of areas identified)	(Number of areas identified)	(Number of areas identified)
Weak Fluorescence	(Number of areas identified)	(Number of areas identified)	(Number of areas identified)
No Fluorescence	(Number of areas identified)	(Number of areas identified)	(Number of areas identified)

Second, these data will also be placed in a simpler 2x2 grid for fluorescence sensitivity/specificity analysis:

Fluorescence vs. Tumor Density	Tumor	No Tumor
Fluorescence	a (Number of areas identified)	b (Number of areas identified)
No Fluorescence	c (Number of areas identified)	d (Number of areas identified)

Sensitivity=a/(a+c); specificity=d/(b+d)

Third, the following grid will be used to examine the sensitivity/specificity of white light examination of the tumor bed and tumor density:

White Light		
Examination vs. Tumor	Tumor	No Tumor
Density		
White Light Obvious	a (Number of areas	b (Number of areas
Tumor	identified)	identified)
White Light Obvious No	c (Number of areas	d (Number of areas
Tumor	identified)	identified)

Sensitivity=a/(a+c); specificity=d/(b+d)

Fourth, the following grid will be used to examine the relationship of the neurosurgeon's intraoperative fluoroscopic aided estimate of the extent of

IRB NUMBER: 12-135

resection vs. the actual extent of resection as measured by post-operative MR imaging techniques (See definitions in section 10.1.1), specifically a Cohen's kappa will be calculated to assess the strength of agreement between operative EOR and MRI EOR:

Operative EOR vs. MRI EOR	MRI GTR	MRI NTR	MRI IR
	(Number of	(Number of	(Number of
Operative GTR	areas	areas	areas
	identified)	identified)	identified)
	(Number of	(Number of	(Number of
Operative NTR	areas	areas	areas
	identified)	identified)	identified)
	(Number of	(Number of	(Number of
Operative IR	areas	areas	areas
	identified)	identified)	identified)

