1. OBJECTIVES

- 1.1 Primary Objectives:
 - 1.1.1 Establish a safe dose for oral 5-ALA administration.
 - 1.1.2 Determine the sensitivity and specificity of 5-ALA mediated fluorescence for malignant glioma tissue in the brain.
 - 1.1.3 Compare the neurosurgeon's intra-operative estimate of the extent of malignant glioma resection (as guided by tumor fluorescence) with the actual extent of resection determined by post-operative imaging.

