4.1.2 Surgical Phase

5-ALA will be mixed in the minimum volume of sterile water or juice immediately before use and given as a single bolus orally approximately three hours prior to induction of anesthesia for surgical resection of a malignant brain tumor. Image-guided microsurgical resection of the tumor will be undertaken. The intensity of the white and blue light from the microscope will be measured at the shortest focal length of the microscope with a digital light meter before resection of the tumor is performed. During tumor resection under the surgical microscope, the tumor bed will be illuminated with deep blue light via a high pass optical filter in the microscopes light chain. The neurosurgeon will examine the tumor bed with a barrier filter in the optical chain of the surgical microscope (see Appendix B).

Under white light the neurosurgeon will take small biopsies from areas of obvious tumor and areas in the wall of the resection cavity that are judged to be normal (but possibly edematous), non-eloquent brain.

Under blue light, small biopsies will be taken from areas of strong fluorescence, weak fluorescence and non-fluorescing regions in the tumor resection cavity.

At all times, the neurosurgeon will use their best judgment to remove or biopsy only that tissue that would normally be removed or biopsied as part of any brain tumor procedure that was not involved or part of an investigational study.

Specimens will be collected regardless of fluorescence. All biopsy specimens, including those taken from the solid tumor, will be reviewed by a neuropathologist. Residual fluorescent tissue in the tumor cavity will be surgically removed only if in the judgment of the neurosurgeon these areas would have been resected using white light alone and that this would lead to a more complete resection of tumor. Pathologic confirmation of tumor type will be made by neuropathology.

After surgical resection of the tumor, the neurosurgeon will judge the extent of resection by estimating the volume of remaining obvious tumor seen under white light or fluorescent tissue seen under blue light.

Data Collection in Operating Room

Under White Light	Obvious Tumor	Obvious Normal Brain (possibly edemator		
Biopsy for Histology	A	В		
Tumor Content of Sample	X	X		
Specimen Labeled	X		X	
Under Blue Light	Strongly Fluorescent Tissue	Weakly Fluorescent Tissue	Non-Fluorescent Tissue	

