Biopsy for Histology	A (This can be the same biopsy as A under white light or it can be a new biopsy D)	С	B (This can be the same biopsy as B under white light or it can be a new biopsy E)	
Fluorescence Intensity by Neurosurgeon	X	X	X	
Tumor Content of Sample	X	Х	X	
Specimen Labeled	X	X	X	
Estimate made of extent	X	X	X	

IRB NUMBER: 12-135

of Fluorescent		
Tissue/Tumor Resected		

Specimens will be collected regardless of fluorescence.

Areas where biopsies have been made of fluorescent and non-fluorescent tissue within the tumor cavity will be graded by the neurosurgeon at the time of biopsy as 0 to +++ (3+) fluorescence. This will be recorded in the operating room each specimen identified with a code. The pathologist who reviews each specimen will be blinded as to the extent of fluorescence in the area where the biopsy was obtained.

Grade	Definition	
0	No fluorescence. No difference between any of the tissues visualized.	No fluorescence
+	Low fluorescence. Red glow is barely distigushed from surrounding non-fluorescent tissue.	Weak fluorescence
++	Moderate fluorescence. Dull red glow of fluorescent tissue.	
+++	High fluorescence. Bright red glow of fluorescent tissue	Strong fluorescence

The neurosurgeon is responsible for:

- An overall assessment of the detection of tumor within the cavity provided by the fluorescence imaging.
- Judging the extent of resection of the tumor or fluorescent tissue.
- Under white light:
 - Identifying at least one area of obvious tumor and biopsying that site.
 Then switch to blue light and grading the fluorescence at the site.
 - Identifying at least one area of obviously normal (but possibly edematous) brain in the wall of the tumor resection cavity in an area of non-eloquent brain and biopsying that site. Then switch to blue light and grading the fluorescence at the site.
- Under blue light:
 - Identifying at least one fluorescent area within the tumor cavity in an area of non-eloquent brain and biopsying and grading that site's fluorescence.
 It may not be necessary to biopsy this area if this same area has already been biopsied under white light.
 - Identifying at least one non-fluorescent area within the tumor cavity in an area of non-eloquent brain and biopsying and grading that site's fluorescence. It may not be necessary to biopsy this area if this same area has already been biopsied under white light.

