12.2 Sample Size/Accrual Rate

It is anticipated that this trial will accrue a mimimum of 3 patients and a maximum of *18 patients in the phase 1 portion of this protocol and 16 patients in the phase 2 portion of the trial. (*Due to four patients receiving 40mg/kg rather than three, 19 total patients will be studied in phase 1. Protocol deviation approved by IRB on 17 Oct 2013.)

Total accrual of a maximum of 34 patients in 48 months is expected.

Assuming that the estimated success rate of resection is 0.70, with a sample size of 34, we will have 80% power to detect a moderate kappa of 0.490 from the null hypothesis of zero intraclass kappa, using a large sample 0.050 level two-sided test.

Descriptive statistics will be presented as mean and standard deviation for continuous variables, as frequency and percentage for categorical variables. SAS 9.1 will be used to perform the statistical analyses, type I error (significance level) will be set as 0.05.

32

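### Does leaving out an interval and a patient-level variance for fluorescence sensitivity and specificity call for a change to the plan?

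*Combined protocol and SAP*

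**What the plan says.** Section 1.1.2 lists as a primary objective: "Determine the sensitivity and specificity of 5-ALA mediated fluorescence for malignant glioma tissue in the brain". Section 12.1.2 restates it for the dose recommended from phase 1.

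The biopsy scheme is in section 4.1.2. Under blue light, "small biopsies will be taken from areas of strong fluorescence, weak fluorescence and non-fluorescing regions in the tumor resection cavity". Under white light the neurosurgeon samples one site of each kind, beginning with "Identifying at least one area of obvious tumor and biopsying that site". The strong and non-fluorescent biopsies may be the white-light ones reused, so a patient gives about three to five areas. Patients with poor fluorescence still contribute: "Specimens will be collected regardless of fluorescence".

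Section 12.1.2 puts these areas in a 3x3 grid, for which "kappa will be calculated to assess the strength of agreement between fluorescence and tumor density". It then says that "these data will also be placed in a simpler 2x2 grid for fluorescence sensitivity/specificity analysis", and a further 2x2 grid does the same for white light. Every cell is labelled as a count of areas. Sensitivity is a/(a+c) and specificity is d/(b+d). The only general statements on inference are in section 12.2: categorical data are given as frequency and percentage, and "SAS 9.1 will be used to perform the statistical analyses, type I error (significance level) will be set as 0.05". The one sample-size calculation there concerns the extent-of-resection kappa.

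**The concern.** Two things look wrong. First, an accuracy claim that is a primary objective has no stated precision. Specificity will rest on few no-tumor areas, so a bare percentage could look firmer than it is. Second, areas from one patient share a tumor, a dose and a surgeon. The textbook expectation is that treating them as independent gives intervals that are too short. The label on the cells is not fully reassuring either, because the extent-of-resection grid carries the same label although Appendix C records one such result per patient.

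At stake is how precise the accuracy claim looks in the report. No dose decision, stopping rule or hypothesis test depends on it.

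**Working it through.** **1. The plan's own figure.** Section 12.2 gives N = 34, kappa 0.490 against 0, two-sided 0.05 and 80% power. For a binary intraclass kappa with null 0, N = (1.960 + 0.842)²/0.49² = 32.7, i.e. 33. Power at 34 is Φ(√34 × 0.49 − 1.960) = Φ(0.897) = 81.5%. The figure reproduces. It does not size sensitivity or specificity.

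**2. Size of the unstated precision.** At least 6 patients at the recommended dose (4.2.1) plus 16 in phase 2 gives 22. As an illustration, assume a true rate of 0.85 and, per patient, two tumor areas and one no-tumor area. The Wilson 95% intervals are:
- sensitivity, 44 areas: 0.72-0.93
- specificity, 22 areas: 0.65-0.95

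Inflating by 1 + (m − 1) × ICC with m = 2 widens the sensitivity interval to 0.70-0.93 at ICC 0.3 (factor 1.3) and 0.68-0.94 at ICC 0.5 (factor 1.5).

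**3. Does the design create positive correlation?** Not necessarily, because sites are chosen by fluorescence class. Take one strong, one weak and one non-fluorescing site, with tumor probabilities 1.00 and 0.922 (biopsy-level values in section 2.3) and an assumed π in the non-fluorescing site, all independent.
- Sensitivity S = 1.922/(1.922 + π): 0.91 at π = 0.2 and 0.79 at π = 0.5.
- True variance per patient ≈ [(1 − S)² × 0.922 × 0.078 + S² × π(1 − π)]/(1.922 + π)².
- Area-level variance per patient = S(1 − S)/(1.922 + π).
- At π = 0.5: 0.0274 against 0.0676, an SD ratio of 0.64.
- At π = 0.2: 0.0293 against 0.0402, an SD ratio of 0.85.

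Here the area-level interval is too wide, not too narrow.

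**4. Simulated coverage of nominal 95% intervals.** The settings are 22 or 34 patients, three or five areas each and latent within-patient correlation 0 or 0.3. The tumor rate is 0.2-0.5 in non-fluorescing and white-light-normal sites, and 0-20% of patients show no fluorescence. Apart from the two section 2.3 rates and the patient numbers, these inputs are assumptions.

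| Quantity | Area-level | Patient-level |
|---|---|---|
| Sensitivity, all patients fluoresce | 96.1-99.9% | within 92.1-96.1% |
| Sensitivity, 20% do not | 93.2-97.1% | within 92.1-96.1% |
| Specificity | 95.8-98.3% | 74.4-93.1% |
| 3x3 kappa | 92.4-96.8% | 93.2-96.1% |

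Area-level means Wilson for the two rates. Patient-level means cluster-robust for the rates and a delete-one-patient jackknife for kappa. The cluster-robust range for sensitivity is over all shares of non-fluorescing patients.

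Area-level half-widths with 22 and 34 patients are 0.08-0.18 and 0.06-0.15 for specificity, and 0.08-0.13 and 0.06-0.10 for sensitivity.

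**5. The layout with reused white-light biopsies** (three areas, two of them chosen under white light): Wilson covers 93.6-98.1% for sensitivity and cluster-robust 90.7-94.8%.

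**6. The cited European study.** Section 2.3 reports 7 false positives in 185 biopsies, so 178/185 = 96.2%, with a 90% interval of 93.0%-98.2%. The exact binomial interval for 178 of 185, with biopsies treated as independent, is 93.0%-98.2%. The biopsy-level interval there is therefore consistent with an ordinary area-level one.

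**The case for a change.** The strongest case for a change is this. The trial is meant to support an approval, and accuracy is a primary objective. Specificity would rest on about 13-38 no-tumor areas with 22 patients, and a sentence costs nothing. The European study quoted in section 2.3 gives both patient-level and biopsy-level predictive values, each with an interval.

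Clustering can also do harm. If tumor areas within a patient are exchangeable and positively correlated (ICC 0.1-0.5, two or three tumor areas each), an interval that ignores patients covers about 82-96%. A variance inflation of 2 alone gives 2Φ(1.96/√2) − 1 = 83%. If 20-40% of patients do not fluoresce and still supply several tumor areas, coverage of sensitivity falls to about 80-90%.

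What stands: the interval is not written down, and a report with bare percentages would be poor. A patient-clustered interval for sensitivity would be a reasonable supplementary analysis.

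What does not stand: the exchangeable model leaves out the selection of blue-light sites by class, which pushes the other way. The documents give neither the share of non-fluorescing patients nor the number of areas they would supply, so even the direction of the effect is open. For specificity the clustered method is clearly worse. No interval removes the dependence of pooled sensitivity on which sites are sampled (0.91 to 0.79 in step 3).

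**Conclusion.** No change follows. This is a gap that an analyst fills sensibly. Section 12.1.2 states the counting unit for the biopsy grids and ties the endpoint to the recommended dose. All four cells are planned, so a 95% interval can be computed from the reported counts without further data. The areas label on the extent-of-resection grid reads as carried over from the grids before it, and Appendix C shows that the count there is one per patient.

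On the choice of method, area-level intervals held 92% coverage or better for sensitivity, specificity and kappa in the simulated settings of steps 4 and 5. The patient-level alternative was no better for sensitivity, worse for specificity and practically equal for kappa. Prescribing a variance rule would settle a debatable choice without a documented gain.

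This rests on assumed tumor rates, a within-patient correlation up to 0.3 and at most 20% of patients without fluorescence. If the data show many non-fluorescing patients with several tumor areas each, the area-level interval for sensitivity would be too short, and the report should say so. Point estimates, the kappa power (81.5% at N = 34) and all decision rules are untouched.

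### The planned sensitivity and specificity of fluorescence depend on how many biopsies each fluorescence class receives, so they do not estimate what primary objective 1.1.2 names

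*Combined protocol and SAP*

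**What the plan says.** Primary objective 1.1.2 reads "Determine the sensitivity and specificity of 5-ALA mediated fluorescence for malignant glioma tissue in the brain". Section 12.1.2 restates it for the recommended dose, places the areas in a fluorescence-by-pathology 2x2 grid and applies "Sensitivity=a/(a+c); specificity=d/(b+d") to the raw counts. No weighting and no interval are described.

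Section 4.1.2 governs where the specimens come from:

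- Blue-light sites are picked by class: "Under blue light, small biopsies will be taken from areas of strong fluorescence, weak fluorescence and non-fluorescing regions in the tumor resection cavity".
- The neurosurgeon's duties include "Identifying at least one fluorescent area within the tumor cavity" and "Identifying at least one non-fluorescent area within the tumor cavity". Neither has a maximum. For weak fluorescence the duty is a single area.
- Two white-light sites are picked as obvious tumour (A) and obviously normal brain (B). They are graded afterwards: "Then switch to blue light and grading the fluorescence at the site".
- The non-fluorescent sample may be shared or new: "This can be the same biopsy as B under white light or it can be a new biopsy E". The strong sample has the same option (A or a new D).
- The section also says "Specimens will be collected regardless of fluorescence".

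Section 12.1.2 appears to put the white-light and blue-light areas in the same grid, but it does not say so outright.

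**The concern.** Fluorescence is the test under evaluation. If sites are sampled by test result, the data estimate directly how often tumour is found within each result class. Sensitivity and specificity run the other way, from true tissue state to test result. To recover them one needs the share of tissue in each class, which the trial does not measure. Without it, a/(a+c) and d/(b+d) mix the behaviour of the dye with the surgeon's choice of how many areas to sample.

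Two series with identical dye behaviour could report different figures for a primary objective. The Appendix C checklist asks which neurosurgeon operated, so more than one is expected and sampling habits may differ. Section 2.3 says that the earlier European study gave nothing on negative predictive value and left real sensitivity open, while calling this less critical for clinical use. A figure labelled sensitivity would look as if it filled that gap.

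**Working it through.** **Plan's own figure.** The plan gives no expected value or precision for sensitivity or specificity. Its only design calculation (34 patients, kappa 0.490) is a power calculation for kappa under an assumed success rate of resection, and does not bear on this point.

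**Inputs.** Section 2.3 gives tumour in 100% of strong and 92.2% of weak specimens. It also gives 185 fluorescing biopsies with 7 false positives, all weak, which implies 90 weak (83 with tumour) and 95 strong. Check with exact 90% limits: 83/90 = 92.2% (85.9 to 96.3), 178/185 = 96.2% (93.0 to 98.2), 95/95 = 100% (lower limit 96.9). All match section 2.3. The tumour rate q in non-fluorescent specimens is not in the documents, so 50%, 30% and 10% are assumed. Rates within a class are taken as equal however the site was chosen.

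**Formulas.** For s strong, w weak and n non-fluorescent areas per patient:

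- a = s + w(83/90), b = w(7/90), c = nq, d = n(1 - q)
- sensitivity = a/(a + c), specificity = d/(b + d)

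Example, 1:1:1 at q = 50%: a = 1.922, b = 0.078, c = d = 0.5. Sensitivity = 1.922/2.422 = 79.4%; specificity = 0.5/0.578 = 86.5%. For 2:1:2: 2.922/3.922 = 74.5% and 1/1.078 = 92.8%.

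**Results** (sensitivity/specificity, %):

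| strong:weak:none | q = 50% | q = 30% | q = 10% |
|---|---|---|---|
| 1:1:1 | 79.4/86.5 | 86.5/90.0 | 95.1/92.0 |
| 2:1:2 | 74.5/92.8 | 83.0/94.7 | 93.6/95.9 |
| 1:1:2 | 65.8/92.8 | 76.2/94.7 | 90.6/95.9 |
| 2:1:1 | 85.4/86.5 | 90.7/90.0 | 96.7/92.0 |

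The first two rows are closest to the forms. The last two are an outer range, in which every patient has one extra area in only one class. Tumour rates within a class are the same in every row. The tumour rate over strong and weak combined is not: it is 1.922/2 = 96.1% at 1:1 and 2.922/3 = 97.4% at 2:1.

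**Against sampling error.** Take 22 patients at the recommended dose (6 + 16), at 1:1:1 and ignoring clustering. Approximate exact 95% intervals at the expected counts are 66 to 89% for sensitivity and 56 to 99% for specificity at q = 50%. At q = 10% they are 84 to 99% and 72 to 99%. All specificity shifts, and the sensitivity shift at q = 10%, lie inside these. At q = 50% the outer sensitivity range (65.8 to 85.4%) is nearly as wide as the interval.

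**Limit of class-wise proportions.** Suppose 10% of B sites and 50% of E sites contain tumour (assumed). The tumour-free proportion is 90% from B alone and 70% from B plus E, since (10 + 50)/2 = 30%. Splitting by origin keeps them at 90% and 50%.

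**The case against.** **The forms leave little freedom.** The operating-room table and the Appendix C checklist have one slot each for strong, weak and non-fluorescent, plus two white-light sites, and the data sheet has six specimen rows. This points to about 1:1:1, or 2:1:2 if D and E are both new and the white-light sites are pooled. That stands, and it makes the outer range an extreme rather than an expectation. It does not rescue the estimate: a strict 1:1:1 makes the ratios repeatable, but treats the three classes as equal shares of tissue.

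**Specimens are taken whatever the fluorescence.** That sentence sets no number per class, so it does not change the dependence.

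**White-light sites are not chosen by fluorescence.** True, but they are chosen as obvious tumour or obviously normal brain. Adding them brings in a second selection and leaves the first in place.

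**The 3x3 grid already shows the class counts.** It does, so a careful reader could derive the class-wise proportions. The plan still presents the column ratios as the answer to a primary objective.

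**Stronger readings that a reader might infer.** One is that several weak areas per patient are expected; at 1:2:1 specificity would fall to 76.3% at q = 50%. The plural wording in sections 4.1.2 and 12.1.2 can simply cover several patients. The surgeon's duty, the table and the checklist all provide for one weak area. Another is that pooling of the white-light sites is settled; the text only implies it. A third is that 22 patients is a ceiling: section 4.2.1 sets six as a minimum, and if the level with four patients (40 mg/kg) became the recommended dose, 4 + 3 + 16 = 23 is possible.

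**Conclusion.** The concern holds as a problem of meaning. Followed exactly, the plan gives figures under objective 1.1.2 that describe the biopsied sample and not the tissue. For the mixes nearest the forms, sensitivity moves by 4.9 points at q = 50% and 1.5 points at q = 10%; specificity moves by 6.3 and 3.9 points. The outer range for sensitivity is 65.8 to 85.4% at q = 50% and 90.6 to 96.7% at q = 10%. These sizes rest on strong and weak rates borrowed from the European study and on an assumed q; the dependence itself rests only on how sites are selected. At 22 or 23 patients most of the shifts are within sampling error, but more patients would not remove them.

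A reader might infer that the trial's conduct or dose finding is affected. The documents do not support that, since no test, threshold or dose decision uses these ratios. The point should be fixed because it concerns a primary objective.

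**What to change.** In section 12.1.2, at the recommended dose:

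1. Report as the main measures the proportion with tumour among strong specimens, the same among weak specimens, and the proportion without tumour among non-fluorescent specimens. Keep strong and weak apart.
2. Count each graded specimen once. Repeat the table by selection origin (WL/T, WL/N, BL), which Appendix C already codes. Assign a specimen that serves both light conditions to its white-light origin, because it was chosen before blue-light grading.
3. Give 95% intervals that allow for several specimens per patient, with the method fixed in advance. One option is Clopper-Pearson with n_eff = (sum of m)^2/(sum of m^2), where m is a patient's number of specimens in that class, and numerator equal to the observed proportion times n_eff. It is conservative; another pre-specified method would also serve.
4. Keep a/(a+c) and d/(b+d) as descriptions of the biopsied sample, printed with the number of specimens per class. State there and under 1.1.2 that they do not estimate tissue-level sensitivity or specificity.
5. State that site choice was the surgeon's and that the class-wise proportions can also vary with site choice within a class.

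The cost is wording and a little analysis code, with no extra biopsies or data. The downside is that true sensitivity and specificity stay unknown. Intervals will also be wide: with one specimen per patient and all agreeing, the lower 95% bound is 0.025^(1/22) = 84.6% with 22 patients and 0.025^(1/23) = 85.2% with 23.
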